#### 5. STATISTICAL METHODOLOGY

## **5.1.** General Methodology

Unless otherwise noted, SAS® software (SAS Institute Inc, Cary, NC; v9 or later) will be used for the generation of all tables, graphs, and statistical analyses. Descriptive summaries for continuous variables will include but not be limited to the number of observations, mean, standard deviation, median, minimum, maximum, first quartile, third quartile, and 95% CI. Descriptive summaries for categorical variables will include the number and percentage of participants in each category.

## **5.2.** Treatment Groups

This is a randomized, DBVC study followed by an OLE period. Data will be summarized based on treatment regimen that was assigned (ITT) or that the participant actually applied (safety).

For analyses in the ITT population and safety population, the treatment groups will be ruxolitinib 1.5% cream BID and vehicle cream BID.

For analyses in the open-label evaluable population, the treatment groups will be ruxolitinib 1.5% cream BID and vehicle cream BID to ruxolitinib 1.5% cream BID.

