## **5.3.2.** Safety Population

All randomized participants who applied study treatment at least once will constitute the safety population. Treatment groups for this population will be determined according to the actual treatment the participant applied on Day 1 regardless of assigned study treatment.

All safety analyses in the DBVC period and throughout the study (from baseline to Week 32) will be conducted using the safety population.

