#### 9.1. General Considerations

The analyses in this section will be provided for the safety population in the DBVC and open-label evaluable population in the OLE period. Cumulative TEAEs across the treatment periods (DBVC and OLE periods) will be summarized. Summary tables may be replaced with listings when appropriate. For instance, an AE frequency table may be replaced with a listing if it only contains a few unique PTs reported on relatively few participants.

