#### 9.2. Adverse Events

#### 9.2.1. Adverse Event Definitions

A TEAE is any AE either reported for the first time or worsening of a pre-existing event after first application of study drug and within 30 days of the last application of study drug. For participants who crossover treatments, the first application date is period-specific, and the end date is 30 days after the last application date in this period, or the first application date in the next period, whichever comes first. Analysis of AEs (as discussed below) will be limited to TEAEs, but data listings will include all AEs regardless of their timing in relation to study drug application.

Adverse events will be tabulated by MedDRA PT and SOC. Severity of AEs will be graded using the NCI CTCAE v5.0 (Grade 1 to 5). The CTCAE reporting guidelines and grading details are available on the Cancer Therapy Evaluation Program website.

The subset of AEs considered by the investigator to be related to study drug will be considered treatment-related AEs. If the investigator does not specify the relationship of the AE to study drug, the AE will be considered treatment-related. The incidence of AEs and treatment-related AEs will be tabulated. Serious AEs will also be tabulated.

Any missing onset date, causality, or severity must be queried for resolution. Unresolved missing causality and severity will be handled according to the following rules:

- An unresolved missing causality will be considered treatment-related.
- An unresolved missing severity will be identified as an unknown severity.

For purposes of analysis, all AEs will be considered TEAEs unless the AE can unequivocally be defined as not treatment-emergent.

Application site reactions are AEs that occur at the site of drug application. A summary of ASRs will be provided.

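### Four baseline-to-Week-32 safety tables keep vehicle participants who start ruxolitinib at Week 16 in the vehicle column, and SAP 6.4 gives open-label duration no period-specific start (minor, wrong as written)

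*SAP*

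**What the plan says.** **Columns.** SAP 5.2 opens with a general rule: "Data will be summarized based on treatment regimen that was assigned (ITT) or that the participant actually applied (safety"). It then names the groups: "For analyses in the ITT population and safety population, the treatment groups will be ruxolitinib 1.5% cream BID and vehicle cream BID". A crossover label appears only for the open-label evaluable population, where "the treatment groups will be ruxolitinib 1.5% cream BID and vehicle cream BID to ruxolitinib 1.5% cream BID".

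SAP 5.3.2 says how a safety-population participant gets a group: it is "determined according to the actual treatment the participant applied on Day 1 regardless of assigned study treatment". It also sets the reach of that population: "All safety analyses in the DBVC period and throughout the study (from baseline to Week 32) will be conducted using the safety population".

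**Adverse events.** SAP 9.1 adds: "Cumulative TEAEs across the treatment periods (DBVC and OLE periods) will be summarized". SAP 9.2.1 sets the treatment-emergent window: "For participants who crossover treatments, the first application date is period-specific", and the window closes 30 days after the last application in the period "or the first application date in the next period, whichever comes first".

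**Tables.** Appendix A of the SAP lists four safety-population tables from baseline to Week 32 that are not limited to participants on ruxolitinib throughout: exposure (3.1.1.3), treatment-emergent events by class and term (3.2.2.1.4), the same by term (3.2.3.1.4) and application site reactions (3.2.3.3.4).

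**Duration.** SAP 6.4 covers exposure in the double-blind (DBVC) period and in the OLE. It starts duration at Day 1 and stops it at the last recorded application in the period concerned. SAP 4.1.1 gives Day 1 a single meaning, the first application of either cream.

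**The concern.** Everyone who enters the OLE receives ruxolitinib. A rule that fixes the column on Day 1 and then runs to Week 32 labels up to 16 weeks of active treatment as vehicle. These four tables are the only ones planned to show all participants over 32 weeks. A reader of the SAP cannot tell whether their vehicle column holds ruxolitinib time and events, or how long each column was followed. The two possible readings distort a comparison in opposite directions: mixing pulls the columns together, while truncating vehicle at crossover pushes them apart.

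The duration wording is a separate, smaller defect. Programmed literally, it would put durations in OLE exposure Table 3.1.1.2 that are longer than the OLE itself.

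**Working it through.** The plan states no figure to reproduce here. The check is a reading of the rules followed by arithmetic. The documents give no OLE entry rate and no event risk, so those inputs are assumptions shown as ranges.

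**1. Which column?** SAP 5.2 gives two groups, SAP 5.3.2 assigns them by Day 1, and the same section extends them to Week 32. A vehicle participant who crosses over is therefore a vehicle participant in all four tables. SAP 9.2.1 sets dates for counting events but names no column, and it says nothing on exposure.

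**2. Ruxolitinib share of vehicle-column time.** About 180 randomized 1:1 gives about 90 on vehicle. Let f be the share who enter and complete the OLE, and d the mean DBVC weeks of those who do not enter. Share = 16f / (32f + d(1 − f)).

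| f | d = 16 | d = 8 |
|---|---|---|
| 0.70 | 1,008/2,448 = 41% | 1,008/2,232 = 45% |
| 0.85 | 1,224/2,664 = 46% | 1,224/2,556 = 48% |
| 1.00 | 1,440/2,880 = 50% | 50% |

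OLE treatment is as needed. If cream is used on half of OLE days (d = 16), the share of on-cream time is 0.5f/(1 + 0.5f), or 26-33%.

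**3. Events if mixed.** Take 16-week risks v on vehicle and r on ruxolitinib, and the same f in both arms. The vehicle column shows 1 − (1 − v)(1 − rf), and the ruxolitinib column 1 − (1 − r)(1 − rf). With f from 0.70 to 1.00:

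| r vs v | 16-week ratio | Ratio shown |
|---|---|---|
| 8% vs 2% | 4.0 | 1.76 to 1.56 |
| 12% vs 10% | 1.20 | 1.10 to 1.08 |
| 22% vs 20% | 1.10 | 1.05 to 1.04 |

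The dilution is large only where the 16-week ratio is large. Even in the first row the risk difference moves only from 6.0 points to 5.7-5.5.

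**4. Events if truncated.** Assume no drug effect, equal 16-week risk p, constant hazard, and a share g = 0.70-1.00 of ruxolitinib participants completing the OLE. The crude ratio is 1 + g(1 − p). For p from 5% to 20% it runs from 1 + 0.70 × 0.80 = 1.56 to 1 + 1.00 × 0.95 = 1.95. With the OLE hazard halved it is 1 + g(1 − p)q/p, where q = 1 − √(1 − p), which gives 1.30-1.48.

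**5. Would exposure-adjusted rates repair this?** With time censored at first event and a constant hazard, the rate ratio is 1.00. With the OLE hazard halved it is [p + g(1 − p)q] / [p + 2g(1 − p)q]. At p = 0.20, g = 0.70 this is 0.2591/0.3182 = 0.81; at p = 0.10, g = 1.00 it is 0.1462/0.1924 = 0.76; at p = 0.05, g = 1.00 it is 0.0741/0.0981 = 0.75. So with no drug effect the rate could favour ruxolitinib by roughly 19-25%.

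**6. OLE duration.** On schedule, Week 16 falls on Day 16 × 7 + 1 = 113. With the last application on Day 224, just before Week 32, duration from Day 1 is 224 days; from the first OLE application it is 224 − 113 + 1 = 112 days.

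**The case against.** **The event content is mostly available elsewhere.** This stands, and it limits the point. The DBVC tables hold vehicle alone, the OLE tables have a crossover column, and 17 tables are restricted to participants on ruxolitinib throughout. For treatment-emergent events by class and term these are 3.2.2.1.1 to 3.2.2.1.3.

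**The SAP clearly means to separate crossovers.** The opening of SAP 5.2 refers to what was actually applied, SAP 4.1.3 resets the OLE safety baseline for crossovers, and SAP 9.2.1 has a period-specific window. That shows intent. It does not override the two-group sentence or the Day 1 rule, and it sets no column for the four tables.

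**The table shells may settle the layout.** They are in a separate document that was not available for this review, so the finished tables may be labelled correctly. The finding concerns the governing text.

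**The duration point is wording only.** Largely so. Tying the last application to the period suggests a period-specific start was meant, and 224 days in an OLE table would be noticed. For Table 3.1.1.3, counting from Day 1 works as it stands; only the scope of SAP 6.4 omits that table.

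**Stronger readings to avoid.** A reader might infer that the plan hides a safety signal or biases its safety conclusions. The documents do not support this: the controlled comparison is in the DBVC tables, and the four tables are descriptive, with no planned ratio or test between columns. A reader might also infer that exposure-adjusted rates are required. They are not: they remove the follow-up difference only under a constant hazard, and as-needed OLE use makes that doubtful.

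**Conclusion.** Minor, but wrong as written. Following SAP 5.2 and 5.3.2 puts ruxolitinib exposure under vehicle in Table 3.1.1.3. It also either mixes the events in the three event tables or, under the SAP 9.2.1 window, sets unequal follow-up side by side. The main size is 41-50% of vehicle-column participant-time. It rests on an assumed 70-100% of vehicle participants entering and completing the OLE and on full DBVC follow-up for the rest. The event ratios are illustrations and depend heavily on the assumed risks. The duration rule, read literally, roughly doubles OLE duration for a participant treated to Week 32, though this was probably not intended. Nothing in the efficacy analysis, the Type I error control, the 16-week safety comparison or the OLE adverse event tables changes.

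**What to change.** **SAP 5.2 and 5.3.2.** For Tables 3.1.1.3, 3.2.2.1.4, 3.2.3.1.4 and 3.2.3.3.4:
- Assign exposure by the treatment at application and events by the treatment at onset.
- Use three columns: vehicle (DBVC only); vehicle to ruxolitinib, from the first OLE application; ruxolitinib from Day 1.
- Show participant-time for each column.
- State that crossover participants appear in two columns and that the DBVC tables remain the controlled comparison.

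**SAP 6.4.** Define duration as first to last application within the period, and add baseline to Week 32 to the section's scope.

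**Check for the same labelling.** Review the table shells and the safety-population laboratory box plots that span the treatment period (4.13.1.1 to 4.13.7.1).

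**Optional.** Exposure-adjusted incidence rates may be added, but only beside the crude percentages and with the constant-hazard assumption stated.

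**Cost.** A few sentences in the SAP, four revised shells and a little programming. Application and onset dates are already collected. The new columns will partly repeat the DBVC and OLE event tables, which is acceptable for a cumulative display.

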## 5.3. Analysis Populations

#### **5.3.1.** Intent-to-Treat Population

All participants who are randomized to the study will constitute the ITT population. Treatment groups for this population will be defined according to the treatment assignment at the time of randomization regardless of the actual study treatment the participant might apply during their participation in the study.

The ITT population will be used for the summary of demographics, baseline characteristics, participant disposition, and analyses of all efficacy data.

## **5.3.2.** Safety Population

All randomized participants who applied study treatment at least once will constitute the safety population. Treatment groups for this population will be determined according to the actual treatment the participant applied on Day 1 regardless of assigned study treatment.

All safety analyses in the DBVC period and throughout the study (from baseline to Week 32) will be conducted using the safety population.

#### 5.3.3. Open-Label Evaluable Population

All participants who applied study treatment at least once during the OLE period will constitute the open-label evaluable population. All safety analyses for the OLE period will be conducted with the open-label evaluable population.

## **5.3.4.** Pharmacodynamic-Evaluable Population

The PD evaluable population includes participants who applied study treatment at least once and provided baseline PD sample and at least 1 postbaseline PD sample for analysis. The study translational scientist will review data listings of participant administration and sample records to identify participants to be excluded from the analysis.

## 6. BASELINE, EXPOSURE, AND DISPOSITION

Appendix A provides a list of data displays. Sample data displays are included in a separate document.

## 6.1. Demographics, Baseline Characteristics, and Disease History

#### 6.1.1. Demographics and Baseline Characteristics

The following demographics will be summarized for the ITT population during the DBVC period and open-label evaluable population in OLE period: age, age group, sex, race, ethnicity, weight, height, and BMI.

## **6.1.2.** Baseline Disease Characteristics

Baseline disease characteristics summarized for the ITT population during the DBVC period include but are not limited to the following:

- Time since initial diagnosis of CHE
- Prior history of asthma (no/yes)
- Prior allergies (food, conjunctivitis, rhinitis) (no/yes)
- History of AD more than 5 years ago (no/yes)
- Type of CHE
- Diagnostic patch test result in the past 3 years (positive, negative, not available)
- CHE related to occupational factors (no/yes)
- Type of occupation if CHE related to occupational factor is yes
- History of skin infection on hands (including wrists) related to CHE requiring antibiotic treatment (no/yes)
- Time since onset of current CHE flare
- Number of CHE flares in the last 12 months
- Prior therapies for CHE received (no/yes)
- Contraindication to oral alitretinoin within the last 12 months (no/yes)
- Skin type using Fitzpatrick classification
- Total %BSA affected with CHE in current flare
- Baseline IGA-CHE score (3, 4)
- Baseline CHE-related Itch NRS score (by visit and daily)
- Baseline CHE-related Skin Pain NRS score (by visit and daily)

## 6.1.3. Prior Therapy for Chronic Hand Eczema

Prior therapies for CHE which include medication and other type of therapies will be coded using the WHO Drug Dictionary and summarized by treatment group. The type of treatment and reason for discontinuation will be summarized as well.

#### 6.1.4. Medical History

For participants in the ITT Population during the DBVC period, medical history will be summarized and listed by assigned treatment groups. This summation will include the number and percentage of participants with medical history event for each body system/organ class as documented on the eCRF.

## **6.2.** Disposition of Participant

The number and percentage of participants who were randomized, treated, and completed the DBVC period and of participants who discontinued the treatment or withdrew from the study during the DBVC period with a primary reason for discontinuation will be summarized for ITT population during the DBVC period.

The number and percentage of participants who completed the OLE period and discontinued treatment or withdrew from the study during the OLE period with a primary reason for discontinuation will be summarized for the open-label evaluable population in the OLE period.

#### 6.3. Protocol Deviations

Protocol deviations will be summarized by treatment groups in the DBVC and OLE periods, separately.

# 6.4. Exposure

For participants in the safety population during the DBVC period and open-label evaluable population in OLE period, descriptive statistics will be provided. That is, by treatment group for duration of treatment, average daily amount of cream applied (g), and total amount of cream applied (g). Duration of treatment with ruxolitinib cream or vehicle cream is defined as the number of days from Day 1 to the last record of ruxolitinib cream or vehicle cream application in the specific period.

# **6.5.** Study Drug Compliance

Overall compliance (%) for the application of ruxolitinib cream or vehicle cream during the DBVC period will be calculated for all participants in the safety population as follows:

overall application compliance (%) =  $100 \times [\text{total number of nonmissing applications}] / [\text{total number of intended applications}],$ 

where the total number of nonmissing applications is the total number of applications that the participant actually applied during the study. The total number of intended applications is the number of planned applications minus the number of interrupted applications.

## 6.6. Prior and Concomitant Medication

For participants in the ITT population during the DBVC period, prior medications and concomitant medications will be coded using the WHO Drug Dictionary and summarized as number and percentage of participants with prior and concomitant medications by WHO drug class and WHO drug term. For participants in the OLE period, only concomitant medications will be summarized.

#### 7. EFFICACY

Appendix A provides a list of data displays. Sample data displays are included in a separate document.

## 7.1. General Considerations

For all continuous variables, both the actual value and change and/or percentage from baseline (if available) will be analyzed.

All by-visit analyses will include the safety follow-up period if the data are available.

## 7.2. Efficacy Hypotheses

Not applicable.

## 7.3. Analysis of the Primary Efficacy Parameters

## 7.3.1. Primary Efficacy Measures

## 7.3.1.1. Investigator's Global Assessment-Chronic Hand Eczema

The IGA-CHE is an overall eczema severity rating on a 0 to 4 scale that will be assessed during site visits. The grades for the IGA-CHE are shown in Table 3.

Table 3: Investigator's Global Assessment-Chronic Hand Eczema

Grade	Severity	Features	Intensity	
0	Clear	Erythema, scaling, hyperkeratosis/lichenification	Absent	
		Vesiculation, edema, fissures	Absent	
1	Almost	Erythema, scaling, hyperkeratosis/lichenification	At least 1 mild	
	clear	Vesiculation, edema, fissures	Absent	
2	Mild	Erythema, scaling, hyperkeratosis/lichenification	At least 1 mild	
		Vesiculation, edema, fissures	At least 1 mild	
3	Moderate	Erythema, scaling, hyperkeratosis/lichenification	At least 1 mild or moderate	
		Vesiculation, edema, fissures	At least 1 moderate	
4	Severe	Erythema, scaling, hyperkeratosis/lichenification	At least 1 moderate or severe	
		Vesiculation, edema, fissures	At least 1 severe	

Source: Adapted from Ruzicka et al 2008.

The IGA-CHE-TS is defined as an IGA-CHE score of 0 or 1 with  $\geq$  2 grade improvement from baseline.

#### 7.3.2. Primary Efficacy Analyses

The key parameters for the primary analysis are provided in Table 4. The primary analysis will be based on the ITT population in the DBVC period. The primary alternative hypothesis (superiority of active ruxolitinib 1.5% cream BID compared with vehicle) will be tested at a 2-sided  $\alpha = 0.05$  level using a CMH test stratified by stratification factors IGA-CHE score (3 or 4) and region (North America or outside of North America). The p-value and overall odds ratio

with 95% CI will be provided. Summary of IGA-CHE-TS rates will be reported for each treatment group. Stratum-adjusted IGA-CHE-TS rate difference (1.5% BID vs vehicle) and 95% CI will be computed using Mantel-Haenszel weights (Mantel and Haenszel 1959).

**Table 4:** Summary of Primary Analysis

Parameter	Definition	
Treatment	Ruxolitinib 1.5% cream compared with vehicle cream	
Population	ITT Population	
Variable	IGA-CHE-TS at Week 16: Defined as an IGA-CHE score of 0 or 1 with ≥ 2 grade improvement from baseline	
Population-level summary	Stratum-adjusted IGA-CHE-TS rate difference with 95% CI	

All nonresponders during the DBVC period, as well as all participants missing Week 16 assessment and who discontinue study treatment at any time before Week 16, or discontinue from the study for any reason, will be defined as nonresponders for the nonresponder imputation analysis.

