6.6.3. Prohibited Medications and Procedures

No rescue treatment or therapy is allowed during the study (see Section 6.5.2). In addition, the following are not permitted during the study:

- Any investigational medication other than the study drug.
- Treatment known to affect the course of CHE.
- Topical corticosteroids; topical calcineurin inhibitors; systemic corticosteroids (except short-term use of systemic corticosteroids to treat an AE during the OLE period, see Section 6.6.2); methotrexate, cyclosporin A, azathioprine and biological therapies, or other immunosuppressant agents; and oral alitretinoin or any other systemic treatment for CHE.
- Strong systemic CYP3A4 inhibitors.
- Phototherapy or tanning beds.
- Live-attenuated vaccination during the DBVC period.

Note: COVID-19 vaccination is permitted.

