7. DISCONTINUATION OF STUDY TREATMENT AND PARTICIPANT WITHDRAWAL

7.1. Discontinuation of Study Treatment

7.1.1. Reasons for Discontinuation

Participants **must** be discontinued from study treatment for the following reasons:

- Disease worsens requiring treatment with prohibited medication. The participant should be discontinued at the discretion of the investigator or based on discussions with the medical monitor.
- The participant becomes pregnant.
- Consent is withdrawn.

Note: Consent withdrawn means that the participant has explicitly indicated that they do not want to be followed any longer; in this case, no further data, except data in the public domain, may be solicited from or collected on the participant. Participants may choose to discontinue study treatment and remain in the study to be followed for disease progression and survival.

- Further participation would be injurious to the participant's health or well-being, in the investigator's medical judgment.
- Unacceptable toxicity as noted in Section 6.5.
- The study is terminated by the sponsor.
- The study is terminated by the local health authority, IRB, or IEC.

A participant **may** be discontinued from study treatment as follows:

- If, after 2 consecutive study visits and reinforcement of study drug application by site staff, a participant's drug usage exceeds one 60-g tube every 4 days; a participant who again fails to meet compliance benchmarks at a subsequent visit may be considered for withdrawal from the study. The medical monitor should be consulted for instruction on handling the participant.
- If, during the course of the study, a participant is found not to have met eligibility criteria, the medical monitor, in collaboration with the investigator, will determine whether the participant should be withdrawn from study treatment.
- If a participant is noncompliant with study procedures or study drug administration in the investigator's opinion, the sponsor should be consulted for instruction on handling the participant.

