10.1. Sample Size Determination

Approximately 180 participants will be randomized 1:1 to ruxolitinib 1.5% cream BID or vehicle cream BID.

The sample size is calculated to provide sufficient power (> 80%) to detect a difference between ruxolitinib 1.5% cream BID and vehicle cream BID for the primary and key secondary endpoints. The powers for different endpoints are provided in Table 9. The chi-square test with a 2-sided α of 0.05 is used to calculate the powers.

In addition to providing sufficient power for efficacy variables, the sample size is determined to provide an adequate database for safety evaluations.

Table 9: Powering for Primary and Key Secondary Endpoints

Variables	Response Rates With Ruxolitinib 1.5% Cream BID	Response Rates With Vehicle Cream BID	Power
IGA-CHE-TS at Week 16	26% ^{ab}	10% ^{abc}	80%
ITCH4 at Week 16	40% ^{bc}	18% ^{bc}	90%
ITCH4 at Week 4	35% ^{bc}	12% ^{bc}	95%
ITCH4 on Day 7	30% ^{bc}	10% ^{bc}	92%

^a Based on the results from a Phase 2b study of topical delgocitinib in CHE (Worm 2022).

^b Based on the results from a Phase 3 study of topical delgocitinib in CHE (Bissonnette 2023).

^c Based on the results from the 2 Phase 3 registrational AD studies, INCB 18424-303 and INCB 18424-304.

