10.4.1. Primary Analysis

The key parameters for the primary analysis are provided in Table 11. The primary analysis will be based on the ITT population. The primary alternative hypothesis (superiority of active ruxolitinib 1.5% cream BID compared with vehicle cream) will be tested at a 2-sided $\alpha = 0.05$ level using a Cochran-Mantel-Haenszel test stratified by IGA-CHE score (3 or 4) and region (North America or outside of North America). A summary of IGA-CHE-TS rates will be reported for each treatment group. The p-value and stratum-adjusted IGA-CHE-TS rate difference with 95% CI will be provided (Mantel and Haenszel 1959).

Table 11: Summary of Primary Analysis

Parameter	Definition
Treatment	Ruxolitinib 1.5% cream compared with vehicle cream
Population	ITT population
Variable	IGA-CHE-TS at Week 16: defined as an IGA-CHE score of 0 or 1 with ≥ 2-grade improvement from baseline
Population-level summary	Stratum-adjusted IGA-CHE-TS rate difference with 95% CI

All nonresponders in the DBVC period, participants who discontinue study treatment at any time before the timepoint of interest, and participants who discontinue from the study for any reason will be defined as nonresponders for the nonresponder imputation analysis. Subgroup analysis by baseline characteristic (eg, IGA-CHE, region, or age) will be performed.

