## 7.4.2. Key Secondary Efficacy Analysis

Key secondary efficacy analyses will be conducted in the ITT population in the DBVC period. If the primary objective is achieved, the statistical comparisons for key secondary endpoints will be tested with the procedures specified in Section 3.2. The same nonresponder imputation method as specified in the primary analysis will be used to handle missing Week 4 and Week 16 itch data.

For the key secondary endpoints of ITCH4 at Week 1 (Day 7), all participants who are missing Day 7 daily Itch NRS scores will be imputed using multiple imputation by fully conditional specification method. The variables to be included in the imputation regression model are treatment group, stratification factor, baseline itch score, and postbaseline daily itch score on Day 1 to Day 7. The corresponding binary response on Day 7 will be derived for each of the imputed datasets per the definition in Section 7.4.1.1.

The following sample SAS code will be used for the MI:

```
proc mi data=mi_wide seed=18424226 nimpute=30 out=impute_itch;
class trt01p strat1 strat2;
var trt01p strat1 strat2 base avald1 avald2 avald3 avald4 avald5
avald6 avald7;
fcs regpmm nbiter=30;
run;
```

All key secondary efficacy analyses will use stratified CMH test similar to the primary efficacy analysis. The summary of key secondary endpoints analysis is also provided in Table 5.

**Table 5:** Summary of Analyses for Key Secondary Endpoints

Parameter	Definition	
Treatment	Ruxolitinib 1.5% cream compared with vehicle cream	
Population	ITT population	
Variables	ITCH4 response at Week 16 ITCH4 response at Week 4 ITCH4 response at Week 1 (Day 7)	
Population-level summary	Stratum-adjusted IGA-CHE-TS rate difference with 95% CI	

Note 1: Participants with missing observed data at the timepoint of interest (Week 4, Week 16), participants who discontinue study treatment at any time before the timepoint of interest (Week 4, Week 16), and participants who discontinue from the study for any reason will be defined as nonresponders. Participants with missing observed data at Day 7 will be imputed using multiple imputation by fully conditional specification method. No rescue therapy or treatment switch is allowed in this study. Note 2: ITCH4 is defined as  $a \ge 4$ -point improvement in CHE-related Itch NRS score from baseline.

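### A participant who uses a prohibited eczema drug but stays on study cream is not counted as a nonresponder and can be scored as a responder

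*SAP*

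**What the plan says.** **Nonresponse.** SAP 7.3.2 counts as nonresponders those observed to fail, those missing Week 16, and those "who discontinue study treatment at any time before Week 16, or discontinue from the study for any reason, will be defined as nonresponders". Protocol 10.4.1 lists observed failures, "participants who discontinue study treatment at any time before the timepoint of interest, and participants who discontinue from the study for any reason". SAP 7.4.2 (Table 5 Note 1) and Protocol Table 12 carry the same triggers to ITCH4 at Weeks 4 and 16. In the SAP, Day 7 uses multiple imputation for missing scores. None of these places names medication use, and neither SAP Table 4 nor Protocol Table 11 has a row for intercurrent events.

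**Rescue.** Table 5 Note 1 says: "No rescue therapy or treatment switch is allowed in this study". Protocol 6.6.3 prohibits, among other things, topical and systemic corticosteroids and the general class "Treatment known to affect the course of CHE". Protocol 6.6.2 permits short systemic corticosteroid courses for adverse events only in the open-label period.

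**Stopping.** Protocol 7.1.1 puts worsening that needs prohibited medication in its mandatory list, but the same bullet adds: "The participant should be discontinued at the discretion of the investigator or based on discussions with the medical monitor". A separate bullet in that list covers unacceptable toxicity, with no discretion wording. Protocol 6.5.2 defines unacceptable toxicity to include such worsening, but its lead-in says only that toxicity may require stopping. Noncompliance with study procedures sits in the optional list, to be handled by consulting the sponsor.

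**Recording.** Protocol 6.6 has all medications from first application entered in the eCRF.

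**The concern.** The nonresponder rule reaches prohibited therapy only through discontinuation. If a participant takes another eczema drug and keeps applying study cream, nothing in the rule fires, and any success obtained with that drug is credited to the randomised arm. The statement that rescue is not allowed governs conduct. It does not say how the participant is analysed when the ban is broken.

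What is at stake is the primary comparison, which has almost no spare power and which gates all three key secondary tests, together with ITCH4 at Weeks 4 and 16. More use on vehicle raises the vehicle rate and shrinks the difference. More use on active does the opposite. A gap noticed only after the primary lock would have to be settled by a sponsor who is by then unblinded (Protocol 10.4.5, SAP 10).

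**Working it through.** **Step 1: which users the rule reaches.**

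- *Worsening that needs prohibited medication.* The mandatory list in Protocol 7.1.1 and the toxicity definition in 6.5.2 point to stopping, and stopping before Week 16 is nonresponse. The discretion sentence and the permissive lead-in point the other way. These passages must be reconciled; which clinical rule is right is not for this review.
- *Self-medication, or a prohibited drug given for another reason (for example a corticosteroid for an adverse event in the blinded period).* Neither mandatory bullet applies as such. At most the optional noncompliance item does. If the participant stays on cream and scores IGA-CHE 0 or 1 with at least 2 grades of improvement, the written rule makes that participant a responder.

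The second group is the firm gap, because it does not depend on how the first is resolved.

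**Step 2: reproduce the planned power.** Inputs from Protocol 10.1 and Table 9: "Approximately 180 participants will be randomized 1:1 to ruxolitinib 1.5% cream BID or vehicle cream BID", so n = 90 per arm; rates 26% and 10%; "The chi-square test with a 2-sided α of 0.05 is used to calculate the powers". With p̄ the mean of the two rates,

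power = Φ{ [ |p1 − p2|√n − 1.96√(2p̄(1 − p̄)) ] / √( p1(1 − p1) + p2(1 − p2) ) }.

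For 0.26 and 0.10, p̄ = 0.18 and √90 = 9.487. The numerator is 0.16 × 9.487 − 1.96 × 0.5433 = 0.453, the denominator is 0.5314, the ratio is 0.852, and power is **80.3%**, against 80% stated.

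**Step 3: add users who stay on treatment.** Assumption: Table 9 gives the rates with such users counted as failures. Then

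observed arm rate = planning rate + (share using and staying on cream) × (share of those who respond because of it).

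Both shares are assumed. For 2% active and 5% vehicle use with 30% responding, the rates are 26 + 2 × 0.30 = 26.6% and 10 + 5 × 0.30 = 11.5%.

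| Use, active / vehicle | Respond because of it | Rates | Difference | Power |
|---|---|---|---|---|
| none | – | 26.0 vs 10.0 | 16.0 | 80.3% |
| 2% / 2% | 30% | 26.6 vs 10.6 | 16.0 | 79.3% |
| 1% / 2% | 30% | 26.3 vs 10.6 | 15.7 | 78.0% |
| 5% / 5% | 30% | 27.5 vs 11.5 | 16.0 | 77.8% |
| 2% / 5% | 30% | 26.6 vs 11.5 | 15.1 | 73.6% |
| 3% / 10% | 50% | 27.5 vs 15.0 | 12.5 | 53.6% |
| 5% / 0% | 50% | 28.5 vs 10.0 | 18.5 | 88.9% |

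Equal use leaves the difference at 16 points but costs a little power, because both rates move closer to 50% and the variance rises. The last row shows the opposite bias: the difference is overstated by 2.5 points.

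No ITCH4 scenario was computed. The mechanism is the same at Weeks 4 and 16, where the reproduced planned power is higher: 95.9% and 90.9%.

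**The case against.** The strongest reply is that the protocol does not leave stopping to discretion. A reader might infer that it does from "The participant should be discontinued at the discretion of the investigator or based on discussions with the medical monitor", but that reading is too strong. Worsening that needs prohibited medication is also defined as unacceptable toxicity in Protocol 6.5.2, and Protocol 7.1.1 lists unacceptable toxicity as a mandatory reason to stop with no discretion attached. On that route the participant stops and becomes a nonresponder. This stands, and it narrows the gap to use without stopping, plus an inconsistency to resolve.

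The second reply is that the larger power losses rest on nothing in the documents. This also stands. Use of a banned drug while staying on cream is a protocol deviation, participants are questioned about other products (Protocol 6.4), and the open-label period gives them a reason to wait. The 54% figure is an extreme, not an expectation. The formula also assumes that every added success would otherwise have been a failure.

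The third is that heavier vehicle use only makes the test conservative. This is true if use runs that way, but the documents do not establish the direction.

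The fourth is that concomitant medications and protocol deviations will be tabulated by arm. That makes use visible, but no analysis rule acts on it.

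Finally, analysing observed outcomes regardless of medication is a recognised strategy. If that is intended, the plan should say so. Counting use as nonresponse is closer to the rule already chosen, under which stopping treatment is itself failure.

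**Conclusion.** The gap is real, but narrower than a quick reading suggests. The SAP and protocol rules count prohibited eczema therapy as nonresponse only if it leads to stopping treatment or leaving the study. Use without stopping, whether by self-medication or for another reason, is analysed on the observed score under any reading of the stopping passages.

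The size is unknown because no rate is given. On the assumed inputs, use that is small or balanced between arms leaves primary power at about 78–79%. Use of 2% on active and 5% on vehicle gives 74%, and the extreme scenario gives 54%. The text aims higher than any of these ("The sample size is calculated to provide sufficient power (> 80%) to detect a difference"), and Table 9 starts at 80%, so there is no margin. The bias can go either way, depending on which arm uses more.

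It would go beyond the documents to conclude that the trial is underpowered for this reason, or that the effect will be diluted. The supportable conclusion is that an outcome-defining rule is missing where it could be written cheaply. It should be written before the primary lock. If use turns out near zero, the rule changes nothing.

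**What to change.** **Wording.** Add to SAP 7.3.2, and to the Week 4 and Week 16 part of Table 5 Note 1: participants who received a Protocol 6.6.3 medication able to affect CHE before the timepoint are nonresponders at that timepoint, whether or not study treatment was stopped. Record this in SAP 11.1, which at present lists no changes to protocol-defined analyses.

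**Qualifying records.** Define them by blinded review before the primary database lock, including any minimum duration and any time window before the assessment. Without a window, one corticosteroid dose in Week 1 would force failure at Week 16. Report the number of participants affected, by arm.

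**Day 7.** State separately how such use before Day 7 is handled. Multiple imputation there covers missing scores only, so the Week 4 and 16 rule should not extend to Day 7 by accident.

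**Protocol.** Reconcile the stopping wording in 6.5.2 and 7.1.1.

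**Cost.** A few lines of SAP text and a blinded review of medication records already in the eCRF; no new data. The downside is some judgement on which records qualify. This is a cheap improvement.
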